## 6.3 MEASURES TO MINIMIZE BIAS: RANDOMIZATION AND BLINDING

Participants who meet all eligibility criteria and consented for study participation will be randomized by notifying the research pharmacy service. A randomization list will be generated by computer generated sequence and will determine whether the subject receives active drug or matched placebo. The randomization procedure will require confirmation of the eligibility criteria to ensure that the integrity of the randomization is maintained. Subjects will be randomized to one of the two treatment arms based on an unrestricted or "fair-coin" randomization procedure.

Randomization will be carried out in STATA using a uniform distribution with a specific random number seed so that the results are reproducible. The research pharmacy service will maintain the randomization list and provide the study drug as appropriate. All participants who complete the informed consent process will be assigned a study identification number. Numbers will be assigned in consecutive order starting with the number 100. This number will be followed with another two-digit number representing the randomization sequence starting at 01. Participants will be referenced by the study identification number.

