**Description of Study Intervention:**

Up to 30 patients will be equally randomized to receive once daily either 10 mg dose of GSK2256294 or placebo enterally for a duration of 10 days.

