## 4 STUDY DESIGN

### 4.1 OVERALL DESIGN

The study is a single site double-blind, placebo-controlled, phase 1b randomized trial to evaluate the safety and preliminary pharmacologic activity of GSK2256294 in patients with

aneurysmal SAH. We hypothesize that inhibition of the sEH enzyme will be safe in patients with SAH, and result in increased EETs availability at the neuroendothelium, eventually leading to reduced neuroinflammation. Up to 30 patients will be equally randomized to receive once daily enteral administration of either 10 mg dose of GSK2256294 or placebo for a duration of 10 days.

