#### 7.2 PARTICIPANT DISCONTINUATION/WITHDRAWAL FROM THE STUDY

Participants are free to withdraw from participation in the study at any time upon request. An investigator may discontinue or withdraw a participant from the study if any clinical AE, laboratory abnormality, or other medical condition or situation occurs such that continued participation in the study would not be in the best interest of the participant

The reason for participant discontinuation or withdrawal from the study will be recorded on the Case Report Form (CRF). Subjects who sign the informed consent form and are randomized but do not receive the study intervention may be replaced.

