## 8.5 PHARMACODYNAMIC EFFECT ASSESSMENTS

### 8.5.1 SAMPLE COLLECTION

Blood samples will be collected from study participants after randomization but prior to administration of the first dose of study drug or placebo, and again on study day 7 and study day 10. For patients with an external ventricular drain (EVD), cerebrospinal fluid (CSF) will be collected at each timepoint as well.

10 mL of blood and 5 mL of CSF will be collected at each time point. If the indwelling external ventricular drain is removed prior to study day 10, CSF samples will be collected on the day of planned removal. In the event of inability to collect CSF due to obstructed catheter, or low intracranial CSF volume, one additional attempt will be allowed within a period of 24 hours.

Blood samples will be collected by the bedside nurse and processed for storage by study personnel. CSF samples will be collected by physician medical staff, from external ventricular drainage access, and then processed for storage by study personnel.

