## 9.2 SAMPLE SIZE DETERMINATION

The total sample size was selected *a priori* based on the need to evaluate and describe the safety profile of the study drug in this patient population.

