### 10.1.4 SAFETY OVERSIGHT

Safety oversight will be under the direction of an independent safety monitor. The ISM will be independent from the study conduct and free of conflict of interest, or measures should be in place to minimize perceived conflict of interest. Unless requested by the safety monitor for the evaluation of the event and in order to ensure an objective evaluation, the safety monitor will be blinded to group assignment. The safety monitor will not be involved in the analysis of data. The safety monitor will not have financial, proprietary, professional, or other interests that may affect impartial, independent decision-making. All SAEs, AEs, and unanticipated problems related to the study will be monitored by the study investigators on an ongoing basis and AEs will be summarized annually after enrollment is complete.

---

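### Fair-coin randomization leaves the number on drug to chance in a safety trial of up to 30 patients (10% risk of 11 or fewer); concealed 1:1 permuted blocks would largely fix it at little cost

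*Combined protocol and SAP*

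**What the plan says.** Section 6.3 (Measures to Minimize Bias: Randomization and Blinding) sets the allocation rule: "Subjects will be randomized to one of the two treatment arms based on an unrestricted or" fair-coin procedure. The list comes from uniform draws in STATA with a fixed seed and is held by the research pharmacy. No blocks, strata, cap per arm or rule for rejecting an unbalanced list is given there or elsewhere.

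The synopsis says "Up to 30 patients will be equally randomized to receive once daily either 10 mg dose of GSK2256294 or placebo", and section 4.1 says "Up to 30 patients will be equally randomized to receive once daily enteral administration".

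Section 9.2 gives no per-arm number, precision or power. It says the total was selected "based on the need to evaluate and describe the safety profile of the study drug". Section 7.2 adds that patients who are "randomized but do not receive the study intervention may be replaced"; it does not say how a replacement gets an assignment.

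**The concern.** Equal randomization can mean equal probability for each patient or equal arm sizes. Section 6.3 delivers only the first, so a reader of the synopsis or section 4.1 who expects 15 per arm would be misled.

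The primary aim is to describe safety on drug in a population not studied before (section 2.3.2). The information for that aim grows with the number of patients exposed, which the plan leaves to chance although it could be fixed within narrow limits. A small placebo arm also matters, because section 3 plans to compare adverse events between the groups. The only formal comparisons are the secondary t-tests in section 9.4.4, and the loss for them is modest.

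**Working it through.** The plan states no per-arm size or imbalance probability, so it has no figure to reproduce.

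**Inputs.** N = 30, the maximum (synopsis, section 4.1); probability 0.5 per patient, independent draws (section 6.3). An event rate of 10% and the CSF subset sizes below are assumptions for illustration.

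**1. Arm sizes under the fair coin.** The number on drug is X ~ Binomial(30, 0.5).
- P(X = 15) = C(30,15)/2^30 = 14.4%
- P(X ≤ 11) = 10.0%; P(X ≤ 10) = 4.9%
- P(19:11 or worse, either direction) = 2 × 0.1002 = 20.0%

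If fewer enrol, the relative imbalance grows: at an assumed N = 20, P(7 or fewer on drug) = 13.2%.

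**2. Safety information by number on drug, n.** The two-sided 95% upper bound after zero events is 1 − 0.025^(1/n). The chance of seeing at least one event of true rate 10% is 1 − 0.9^n.

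| n on drug | Upper bound, zero events | P(at least one event) |
|---|---|---|
| 10 | 30.8% | 65% |
| 11 | 28.5% | 69% |
| 15 | 21.8% | 79% |
| 19 | 17.6% | 86% |

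**3. Between-arm comparison.** Efficiency relative to 15:15 is 4k(30 − k)/900 with k on drug.
- 19:11: 4 × 11 × 19/900 = 0.929, a loss of 7%; standard error × 1/√0.929 = 1.038
- 20:10: 4 × 10 × 20/900 = 0.889, a loss of 11%; standard error × 1.061
- Average over all splits: 1 − 1/30 = 0.967, a loss of 3.3%

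**4. Arm sizes under permuted blocks.** Blocks of 4 and 6 chosen with equal probability, last block truncated, exact recursion:
- N = 30: 14, 15 or 16 on drug with probability 11.4%, 77.3% and 11.4%; nothing worse can occur
- N = 29: 13, 14, 15 or 16 on drug with probability 1.0%, 49.0%, 49.0% and 1.0%, so 16:13 arises in 2% of lists

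**5. CSF endpoints.** Section 8.5.1 limits these to patients with a drain: "For patients with an external ventricular drain (EVD), cerebrospinal fluid (CSF) will be collected at each timepoint as well". The plan does not give their number, so a range is assumed. The fair-coin figure is 2 × P(Binomial(m, 0.5) ≤ 4). The block figure takes a random subset of m from the 30 and averages the hypergeometric probability over the splits in step 4.

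| CSF patients, m | P(an arm has 4 or fewer), fair coin | Blocks of 4 and 6 |
|---|---|---|
| 12 | 39% | 27% |
| 15 | 12% | 3% |
| 18 | 3% | 0.1% |

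The block column assumes that CSF availability is unrelated to list position. Blocking helps here but does not guarantee balance.

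**The case against.** Simple randomization is valid, was chosen explicitly, and is fully unpredictable, which has value at a single site. The imbalance is symmetric: 19 or more on drug is as likely as 11 or fewer and improves the safety description, and about 80% of lists (1 − 0.2005) have 12 to 18 on drug. Averaged over all lists, the chance of seeing an event of rate 10% is 1 − 0.95^30 = 78.5%, against 79.4% with 15 fixed; the average zero-event bound is 22.4% against 21.8%. No stated target is missed, since section 9.2 sets none and section 9.4.3 analyses safety by tables and clinical review. Balance at randomization does not secure balance in the t-tests, which use only patients who complete 10 days (sections 9.3 and 9.4.4).

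These points are correct and limit the weight. They do not remove the point: the trial is run once on one list, and about one list in ten has 11 or fewer on drug.

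A second objection is that blocks make a revealed assignment informative about its neighbours. Section 10.1.4 keeps the safety monitor blinded with an exception: "Unless requested by the safety monitor for the evaluation of the event". The study number also shows the randomization sequence (section 6.3). The risk is real but small, given matched capsules, a pharmacy-held list, a monitor independent of study conduct, and block sizes that vary and are not disclosed.

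**Conclusion.** The concern holds as an inefficiency and an ambiguity in wording; the fair coin introduces no bias. At N = 30 it carries a 10.0% chance of 11 or fewer on drug and a 20.0% chance of 19:11 or worse in either direction. The average cost is small, and the case for change is that the bad lists can be ruled out at almost no cost. The arm-size figures assume that all 30 enrol, and the CSF figures rest on assumed subset sizes. The change is worth making but is not essential to the trial's validity.

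**What to change.** In section 6.3, replace the fair-coin sentence with wording such as: *Subjects will be randomized 1:1 using permuted blocks of randomly varying size, generated in STATA from a fixed seed. The list, seed and block sizes are held only by the research pharmacy or an unblinded statistician and are not disclosed to investigators.* Do not state the block sizes in the protocol; the 4 and 6 used above are for illustration.

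In the synopsis and section 4.1, write *randomized 1:1* in place of the present phrase. In section 7.2, state that a replacement takes the next assignment on the list. Balance will be near-exact: each untreated patient who is replaced can shift the treated split by one.

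The cost is a few lines of list-generation code and these text edits, with no added patients or visits. The Statement of Compliance requires IRB approval before an amendment is implemented, so the edits are best bundled with another amendment. The document is version 3.0 and does not show whether a list is already in use. If one is, someone unblinded should check its split first, and blocks could then apply only to assignments not yet made.

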#### 6.4 STUDY INTERVENTION COMPLIANCE

Study drug administration will be recorded in the electronic medical record (EMR), which will be used as source documentation, and administration verified daily. Missed doses and reason will be recorded on a study log. The drug accountability record will be maintained by the investigational pharmacy.

#### 6.5 CONCOMITANT THERAPY

Relevant concomitant medications prescribed during the study drug administration period will be recorded from the EMR in the following classes: vasopressors, antihypertensives, hyperosmolar therapy, nimodipine, insulin, statins and antibiotics.

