a cerebral aneurysm. An individual who meets any of the following criteria will be excluded from participation in this study: evidence of prolonged QTc >500 milliseconds, baseline AST and ALT > 2x normal reference values, administration of strong inducers/inhibitors of CYP3A4, symptom onset compatible with SAH of  $\geq 3$  days prior to admission to Oregon Health and Science University Neurosciences Intensive Care Unit (OHSU NSICU), unable to speak or understand English or Spanish, current pregnancy based on urine HCG positive pregnancy test, preexisting severe neurologic deficit or condition, chronic renal failure requiring dialysis, severe terminal disease with life expectancy <6 months, or refusal of informed consent.

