### **Pharmacokinetics and product metabolism**

In human and animal studies, the oral bioavailability of GSK2256294 was generally high, indicating good absorption, low plasma clearance and a half-life of 20-30 hours. Steady state was achieved within 6-8 days after daily repeat dosing in humans.[12] GSK2256294 has low to moderate protein binding, high passive permeability, and a moderate volume of distribution. Structural information on GSK2256294 metabolism in humans following both single and repeat oral doses in both healthy volunteers and obese smokers indicated GSK2256294 was the major drug related component in human plasma with biliary and urinary metabolites being formed by either oxidation with or without subsequent glucuronidation and N-demethylation. Similar metabolites were detected in human and nonclinical hepatocytes.

In vitro data indicated limited potential for GSK2256294 to be a perpetrator of cytochrome P450-mediated drug interactions. Population-based physiologically based pharmacokinetics model simulations, evaluating the risk of an interaction between GSK2256294 and a strong CYP3A4 inhibitor, predicted a moderate increase (3.2 fold) to the mean systemic exposure of GSK2256294 when administered together. Co-administration of strong inhibitors and inducers of CYP3A4 has been recommended to be prohibited.

GSK2256294 inhibited the human breast cancer resistance protein and organic anion transporting polypeptide 1B1 in vitro, suggesting the potential for drug interactions with statins that have their disposition modulated by these transporters. However, a physiologically based pharmacokinetic population based drug-drug interaction modelling simulation between GSK2256294 and sensitive substrates (including rosuvastatin) has predicted the clinical interaction risk to be negligible (<1.05 fold). Hence monitoring of adverse events is recommended with the concomitant use of GSK2256294 with statins.

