## 5.2 EXCLUSION CRITERIA

An individual who meets any of the following criteria will be excluded from participation in this study:

- Symptom onset compatible with SAH of > 3 days prior to admission to OHSU

Evidence of QTc prolongation > 500ms on admission  
Baseline AST and ALT > 2x normal reference range  
Administration of any of the following inducers/inhibitors of CYP3A4: ritonavir, indinavir, nelfinavir, saquinavir, clarithromycin, telithromycin, chloramphenicol, ketoconazole, itraconazole, nefazodone, cobicistat or enzalutamide.  
Current pregnancy, based on urine HCG positive pregnancy test  
Preexisting severe neurologic deficit or condition  
Chronic renal failure requiring dialysis  
Severe terminal disease with life expectancy <6 months  
Unable to read or understand written or spoken English or Spanish  
Refusal of informed consent

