### 7 STUDY INTERVENTION DISCONTINUATION AND PARTICIPANT DISCONTINUATION/WITHDRAWAL

#### 7.1 DISCONTINUATION OF STUDY INTERVENTION

Discontinuation from drug or placebo administration does not mean discontinuation from the study, and remaining study procedures should be completed as indicated by the study protocol. All patients are expected to complete the treatment course unless they experience an SAE that is thought to be related to the study drug, die, are discharged early, or withdraw early from the study.

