### 8.4 SAFETY ASSESSMENTS

#### 8.4.1 DAILY ASSESSMENTS

Daily assessments will be performed beginning on the randomization day (day=1), and on subsequent study days that subjects receive study drug (days 2-10). The randomization day will be defined as the time from randomization to the next 6:59 AM. All subsequent study days will be defined as a 24-hour window between 7:00AM and 6:59 AM the following day. Study staff will perform daily assessments from data collected from the medical record as part of patients' routine intensive care unit treatment and monitoring, or by patient interview. These include:

- **Vital Signs:** every four hour vital signs including blood pressure from noninvasive and arterial sources, heart rate, body temperature, and the presence of absence of mechanical ventilation;
- **Cardiac Monitoring:** daily QTc interval, and the presence of cardiac arrhythmias on continuous EKG monitoring.
- **Intake and Output:** total fluids administered and total drain and urine output;
- **Laboratory Assessments:** serum sodium, blood glucose, BUN, creatinine, hematocrit, peripheral white blood cell count;
- **Neurologic Assessments:** GCS, MCA transcranial Doppler velocities and Lindegaard ratios, and headache severity;
- **Concomitant medications:** Daily administration of selected classes of hospital administered concomitant medications will be reviewed for all study subjects during the first 10 days.

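### In the text shown, no rule carries the recommended bar on strong CYP3A4 inhibitors and inducers through study days 1-10, and sections 1.1 and 5.2 word the entry exclusion differently

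*Combined protocol and SAP*

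**What the plan says.** **The hazard.** Section 2.2 (Pharmacokinetics and product metabolism) gives the recommendation: "Co-administration of strong inhibitors and inducers of CYP3A4 has been recommended to be prohibited". It rests on a simulation with a strong inhibitor that "predicted a moderate increase (3.2 fold) to the mean systemic exposure of GSK2256294 when administered together". No figure is given for inducers.

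**Entry.** The synopsis (1.1) excludes "administration of strong inducers/inhibitors of CYP3A4", that is, the class. Section 5.2 reads "Administration of any of the following inducers/inhibitors of CYP3A4" and then names twelve drugs: ritonavir, indinavir, nelfinavir, saquinavir, clarithromycin, telithromycin, chloramphenicol, ketoconazole, itraconazole, nefazodone, cobicistat and enzalutamide. It neither refers to the class nor marks the names as examples.

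**Dosing period.** Section 6.5 records seven classes: "vasopressors, antihypertensives, hyperosmolar therapy, nimodipine, insulin, statins and antibiotics". Section 8.4.1 adds: "Daily administration of selected classes of hospital administered concomitant medications will be reviewed for all study subjects during the first 10 days". It does not name the classes. Section 7.1 says: "All patients are expected to complete the treatment course unless they experience an SAE that is thought to be related to the study drug", with death, early discharge and early withdrawal as the other exceptions. Section 7.2 lets the investigator discontinue a participant for an adverse event, a laboratory abnormality, or where some "other medical condition or situation occurs such that continued participation in the study would not be in the best interest of the participant".

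**The concern.** The recommendation concerns co-administration, which happens while study drug is being given. The only operative restriction, in 5.2, is an eligibility criterion. If even one of the twelve named drugs were started on day 2, no section shown says that it is prohibited, that study drug should be held, or that the patient should be flagged.

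Safety is the primary endpoint. Section 2.3.1 describes the safety database as limited, and section 2.3.2 says this is the first use in critically ill patients. Strong CYP3A4 inhibitors and inducers are not a recorded class, so whether an exposure is captured depends on the drug falling into one of the seven listed classes. Sections 8.5.1 to 8.5.4 plan no study-drug concentrations, so altered exposure could not be confirmed later.

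The entry mismatch is a smaller matter. Staff working from the synopsis and staff working from 5.2 apply differently worded rules, and section 6.3 requires eligibility to be confirmed before randomization.

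**Working it through.** **Text comparison**

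| Section | Scope | Applies when | Effect |
|---|---|---|---|
| 2.2 | Strong inhibitors and inducers, as a class | Co-administration | Recommendation to prohibit |
| 1.1 | Same class | Entry | Exclusion |
| 5.2 | Twelve named drugs | Entry | Exclusion |
| 6.5 | Seven classes, CYP3A4 drugs not among them | Dosing period | Recording only |
| 8.4.1 | Selected classes, not named there | Days 1-10 | Review only |
| 7.1 | Four exceptions, none an interaction | Dosing period | Completion expected |
| 7.2 | Any situation against the participant's interest | Any time | Investigator discretion |

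Section 6.1.2 adds that missed doses are given as soon as feasible. It has no hold rule.

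**Illustration of size.** The plan gives no figure of its own for this.

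Inputs: 10 mg daily for 10 days (4.1); half-life 20-30 h and a 3.2-fold mean exposure (2.2); highest repeat dose studied, 18 mg daily for 14 days (2.2, Pharmacodynamics and Dose Finding); approximate dose proportionality over 6-20 mg (4.3).

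Assumptions: one compartment, immediate absorption, and an inhibitor that acts only on clearance and is fully effective from its start day.

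Formulas: k = ln 2 / half-life, replaced by k/3.2 once the inhibitor starts. The post-dose amount on day d is A(d) = 10 + A(d-1) x exp(-24k). The 24-hour AUC is A(d) x (1 - exp(-24k)) / k, up to a constant volume that cancels in ratios. A ratio to the uninhibited schedule, times 10 mg, is a dose equivalent.

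Day 1 start, half-life 20 h:
- k = 0.0347 and k/3.2 = 0.0108, so the fraction left after 24 h is 0.435 without and 0.771 with the inhibitor.
- Day-10 post-dose amount: 17.70 without, 40.44 with. Peak ratio 40.44/17.70 = 2.28.
- Day-10 AUC: 288.5 without, 854.7 with. Ratio 2.96.
- Ten-day AUC ratio: 2.39.

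Day 1 start, half-life 30 h: peak ratio 51.74/23.40 = 2.21, day-10 AUC ratio 2.64, ten-day AUC ratio 2.09.

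Dose equivalents in mg; each range covers half-lives of 20 and 30 h:

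| Inhibitor starts | Day-10 24-h AUC | Day-10 post-dose peak | Ten-day average | Days above same-day exposure on 18 mg |
|---|---|---|---|---|
| Day 1 | 26-30 | 22-23 | 21-24 | 6-8 |
| Day 4 | 25-28 | 20.5-21.5 | 17-19 | 4-5 |
| Day 7 | 20-23 | 17-18 | 13-14 | 1-2 |
| Day 9 | 15-17 | about 13 | 11 | 0 |

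The full steady-state equivalent, 10 x 3.2 = 32 mg, is not reached within ten days. For a day 1 start, cumulative AUC through day 10 is 0.79-0.92 of that from 18 mg given for 14 days. If the inhibitor continues until study drug has washed out, the ratio is 3.2 x 10 x 10 / (18 x 14) = 320/252 = 1.27.

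One exposed patient would be 1/15 = 6.7% of a nominal 15-patient active arm. That is an arithmetic share and not an expected rate, and the unrestricted randomization in 6.3 does not fix the arm at 15.

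**The case against.** **The rule may sit elsewhere.** Section 2.3.2 says participation alters clinical care only as set out in the Section 11 schedule. A bar on clinically ordered drugs would alter care, so the schedule is where one might expect it, and Section 11 refers to an attachment that is not shown. This stands. A reader might infer that the whole plan lacks the restriction, but the documents support only the narrower statement that the visible sections do not contain it.

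**The named list may be adequate.** Turning a summary phrase into a list that can be checked is ordinary drafting. A reader might infer that 5.2 lets other strong inhibitors or inducers through. The documents name no such drug, so they do not show the list to be incomplete; they show only that the two rules differ.

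**Staff are not told to dose through an interaction.** Section 7.1 states an expectation, and 7.2 is broad enough to cover stopping study drug. This stands as a limit. But 7.2 does not mention interactions or ask anyone to look for them.

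**Harm is not shown.** Section 2.2 reports no increase in adverse event reporting with dose in single-dose cohorts, and good tolerability in animals up to 600 mg/kg/day (rat) and 1000 mg/kg/day (monkey). Section 2.3.1 reports repeat-dose event frequency similar to placebo, with only a non-significant dose-related trend in HDL. Section 2.3.2 calls the interactions minimal. Daily QTc, continuous ECG, daily laboratory tests and day-7 liver tests are planned (8.4.1, 8.4.2). The day 1 scenario also needs the drug to start at about randomization, since a named drug already in use excludes the patient. All of this stands and limits the severity.

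**Conclusion.** The point holds for the text shown. The protocol reports a recommendation to prohibit a co-administration, applies it at entry in two differently worded forms, and states no rule for the ten days in which the co-administration could occur. Followed as written, these sections permit it, subject to the discretion in 7.2.

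The size is modest and depends on timing. Only an early start puts average exposure clearly above the 18 mg repeat dose; a late start matters little. The figures rest on one simulated mean fold-change and a simple model, and above 20 mg they assume dose proportionality beyond the stated range. A reader might take 26-30 mg as a peak concentration equivalent; it is a 24-hour AUC equivalent, and the modelled peak is about 22-23 mg. The documents establish neither how often this would happen nor any resulting harm.

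On the inhibitor side the threat to the pharmacodynamic result is small, because section 2.2 already reports more than 95% enzyme inhibition after a single 10 mg dose. The inducer side cannot be sized from the documents. Overall this is a minor to moderate safety correction.

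**What to change.** First check whether the Section 11 schedule, manual of procedures or variable list already carries the restriction. Even if one does, the sections below should agree with it.

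- **5.2:** use the synopsis class wording and give the twelve drugs as examples.
- **6.5:** prohibit strong CYP3A4 inhibitors and inducers during study days 1-10, and add the class to the medications recorded daily, which also serves the review in 8.4.1.
- **7.1:** add clinical need for such a drug as a reason to hold or stop study drug. Which of the two applies is for the sponsor and investigators to decide.
- **Safety listings (9.4.3):** flag exposed patients.

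The cost is a few lines of text and one more class abstracted from the medical record. The downside is possibly a few more exclusions or stopped courses. A patient whose course is stopped also leaves the per-protocol population used for the secondary endpoints (9.3).
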